13.6 Pregnancies

Any pregnancy that occurs during study participation should be reported by the site. To ensure patient safety, each pregnancy must also be reported to Novartis within 24 hours of learning of its occurrence. The pregnancy should be followed up to determine outcome, including spontaneous or voluntary termination, details or birth, and the presence or absence of any birth defects, congenital abnormalities or maternal and newborn complications.

Pregnancy should be recorded on a Clinical Study Pregnancy Form and reported by the investigator to the Novartis Drug Safety and Epidemiology (DS&E) department. Pregnancy follow-up should be recorded on the

same form and should include an assessment of the possible relationship to the Novartis study treatment of any pregnancy outcome. Any SAE experienced during pregnancy must be reported on the SAE Report Form.

14. Study Oversight

The study protocol will be reviewed and approved by the National Institutes of Health (NIH) before submission to individual center IRBs for approval. Participant enrollment may only begin with IRB approved consent forms.

Auditing procedures will be followed to ensure that the study is conducted, documented, and reported in accordance with the IRB approved protocol, Good Clinical Practice (GCP) Guidelines, and applicable regulatory requirements of collaborating sites. Verification of eligibility and appropriate documentation of informed consent/assent will be performed for a sample of subjects enrolled in the study. The investigator must maintain source documents for each patient in the study, consisting of case and visit notes (hospital or clinic medical records) containing demographic and medical information, laboratory data, and the results of any other tests or assessments. All information on CRFs must be traceable to these source documents in the patient's file. The investigator must also keep the original informed consent form signed by patient (a copy is given to the patient).

15. Data and Safety Monitoring Committee (DSMC)

The Study Chair has primary oversight responsibility of this clinical trial. The appointed Data and Safety Monitoring Committee (DSMC) has oversight responsibility of the Data and Safety Monitoring Plan (DSMP) for this clinical trial. Each site's Principal Investigator and their research team (co-Investigators, research nurses, clinical trial coordinators, and data managers) are responsible for identifying adverse events. Aggregate report - detailed by severity, attribution (expected or unexpected), and relationship to the study drug/study procedures – will be available from the DMCC for site review. Adverse events will be reviewed by the research team at time of occurrence and reviewed at monthly team meetings.

The DSMC is an internally appointed group of individuals who will monitor and evaluate the safety of the proposed clinical trial. The DSMC's primary role is to ensure the safety of patients in the study. The DSMC will follow the NIH's published guidelines regarding its function and may provide input such as the recommendation to stop the trial for safety reasons. Due to the signal-seeking nature and the small sample size in this study, there is no formal efficacy interim analysis planned. However, the DSMC will review adverse events and serious adverse events and provide a report to the group bi-annually. The DSMC will include individuals familiar with everolimus administration and clinical trial design and will be comprised of [name]. (pediatric neurologist from Boston Children's Hospital), [name]. (pediatric neurologist at Stanford University, Chairperson), and [name]. (biostatistician from the University of North Carolina).

[name]. (Cincinnati Children's Hospital Medical Center) will be the independent medical review officer for this trial. He is an expert in the use of mTOR inhibitors in children and adults with TSC. [name] will review any adverse events/serious adverse events throughout and will also determine if unblinding and reporting to the FDA and DSMC is required. If [name] is unable to fulfill his duty at any point during the study, [name]. (Boston Children's Hospital) will serve as the back-up medical review officer until [name] returns to his duties.

16. Data Management and Coordinating Center and Database

All study data will be collected via systems created in collaboration with the Rare Diseases Clinical Research Network Data Management Coordinating Center (RDCRN DMCC) and will comply with all applicable guidelines regarding patient confidentiality and data integrity.

16.1 Registration

Registration of participants on this protocol will employ an interactive data system in which the clinical site will attest to the participant's eligibility as per protocol criteria and obtain appropriate informed consent. IRB approval for the protocol must be on file at the DMCC before accrual can occur from the clinical site.

The DMCC will use a system of coded identifiers to protect participant confidentiality and safety. Each participant enrolled will be assigned a local identifier by the enrollment site. This number can be a combination of the site identifier (location code) and a serial accession number. Only the registering site will have access to the linkage between this number and the personal identifier of the subject. When the participant is registered to participate in the study, using the DMCC provided web-based registration system; site personnel will insert the unique ID generated from the National Database for Autism Research (NDAR) Global Unique Identifier (GUID) software program, explained in the following section 16.2, as the participant ID number. Thus each participant will have two codes: the local one that can be used by the registering site to obtain personal identifiers and a second code designated by the NDAR GUID. For all data transfers to the DMCC both numbers will be required to uniquely identify the subject. In this fashion, it is possible to protect against data keying errors, digit transposition or other mistakes when identifying a participant for data entry since the numbers should match to properly identify the participant. The only personal identifier accessible to the DMCC is participants' date of birth, as well as the date of onset for all recorded medical events. The database will not collect any other components of a participant's protected health information.

If the subject is participating in more than one DSC study, such as this study and the DSC "Natural History Study of Individuals with Autism and Germline Heterozygous PTEN Mutations" study, data from those studies can be linked.

16.2 Data Elements

Every individual who provides consent will be assigned a Global Unique Identifier (GUID). The GUID is a unique universal subject ID that allows researchers to share data specific to a study participant without exposing personally identifiable information. A member of the research team will enter private health information (PHI) collected from each study participant into the National Database for Autism Research (NDAR) GUID software program. The software performs a one-way encryption of these data, de-identifying and randomizing the data to produce a digital "fingerprint". The GUID program at NIH converts this digital fingerprint into a final GUID that is completely devoid of PHI. The final GUID is returned to the research team as a unique identifier for the participant.

16.3 Data Entry

Data collection for this study will be accomplished with online electronic case report forms. Using encrypted communication links, online forms will be developed that contain the requisite data fields. The DMCC, in collaboration with DSC, is also responsible for data sharing with the NIH National Database for Autism Research (NDAR) and the database of Genotypes and Phenotypes (dbGaP).

All dosing data will be entered into the DMCC database within 24 business hours of the study visit to ensure the most up-to-date information is available for dose modification and participant safety decisions.

16.4 Laboratory Data Flow

Samples collected as a part of this study will be tracked utilizing the corresponding data collection sheets. These forms will be kept both locally and in the database to ensure that samples are sent to the appropriate laboratories. Samples results will be reported electronically to study sites directly from LabConnect. Additionally, the DMCC will data transfer from LabConnect electronically on a regular basis. All transactions are logged and validated for both methods.

16.5 Data Quality and Monitoring Measures

As much as possible data quality is assessed at the data entry point using intelligent on-line data entry via visual basic designed screen forms. Data element constraints, whether independent range and/or format limitations or 'relative' referential integrity limitations, can be enforced by all methods employed for data input. QA reports assess data quality post-data entry. As we note, data quality begins with the design of the data collection forms and procedures and incorporates reasonable checks to minimize transcription and omission errors. Of the more important quality assurance measures are the internal validity checks for reasonableness and consistency.

• Data Monitoring: The RDCRN DMCC will utilize the Data Quality Module within REDCap to identify missing or unclear data. Study sites will be able to generate queries and resolve for their site.

• Data Delinquency Tracking: REDCap will allow the consortium sites to monitor data delinquency on an as needed basis.

16.6 Quality Control Method

Standardized data collection and management procedures will be followed to ensure data quality control. Data will be scored, reduced, and managed on an ongoing basis. The PIs will assume responsibility for uniformity across sites and will coordinate on a weekly basis (or more frequently if needed) with the data collection and management team. After data have been collected, it will be entered into the RDCRN DMCC database. As much as possible, data quality is assessed at the data entry point using intelligent on-line data entry via visual basic designed screen forms. Data element constraints, whether independent range and/or format limitations or 'relative' referential integrity limitations, can be enforced by all methods employed for data input. QA reports assess data quality post-data entry. As we note, data quality begins with the design of the data collection forms and procedures and incorporates reasonable checks to minimize transcription and omission errors. Of the more important quality assurance measures are the internal validity checks for reasonableness and consistency.

All variables will be checked for out-of-range values and the marking of missing values.

17. Data Analysis Plan, Statistical Power and Sample Considerations

This is an exploratory study to evaluate the short-term safety and preliminary efficacy of everolimus in patients with a PTEN mutation. The analyses will be predominantly descriptive with the intent of generating plausible hypotheses to be tested in a Phase III confirmatory trial. Efficacy will be assessed using recognized measures of intellectual ability and neurobehavioral processes.

In objective 1, we will examine the safety and tolerability of everolimus by comparing the 1) dropout rates due to side effects, 2) dropout rates for any reason, and the 3) frequency of specific side effects in those receiving everolimus versus placebo. Based on the published literature and our experience in the tuberous sclerosis trial. we predict that the dropout rates due to side effects will be very similar across everolimus and placebo groups (<10% difference). However, we predict that everolimus will cause higher rates of medication-related side effects (≥10% difference) when compared to placebo. We will use chi-square statistics (or Fisher's exact test depending on cell counts) to compare dropout and rates of specific side effects. Statistical significance will be determined using a one-tailed test Type 1 error rate of α=.05, as only increases with everolimus treatment are expected. No false discovery rate correction will be applied because the concern is maximizing sensitivity to any increase in side effect prevalence with everolimus treatment. For dropout rates, we will also compute Kaplan-Meier survival analyses with discontinuation due to side effects or any reason as separate status endpoints. Number of days from baseline to medication discontinuation will be the time variable. Survival analyses are expected to be under-powered due to the generally low dropout rates expected, but these analyses can be useful for describing temporal trends. To ensure any observed group differences are not influenced by other variables or randomization imbalance, cox and logistic regression analysis will also be conducted with and without conditioning on relevant baseline covariates (e.g., demographics, language and cognitive ability, symptom severity).

In objective 2, we will examine whether the everolimus group will show more improvement, compared to the placebo group, on the main neurocognitive efficacy composite outcome. Randomization Group (everolimus versus placebo) differences on the neurocognitive composite will be analyzed using mixed effects (growth curve) modeling, fully utilizing repeated measurements collected at three points (Time: baseline, 3-month follow-up, and 6-month follow-up). A significant interaction between Time and Randomization Group, with the everolimus group showing a more favorable outcome trajectory, will support the primary efficacy hypothesis. Maximum likelihood estimation will be implemented in the Mplus program version 7.2 or above.

Mixed effects (growth curve) model analyses will be conducted following the intention-to-treat principle. Data points that are missing due to subject attrition will be handled assuming that data are missing at random (MAR) conditional on observed information, which is less restrictive than missing completely at random (MCAR) assumed in fixed effects analyses such as ANCOVA and regression analysis. In this procedure, all available cases including the ones with missing information will be included in the analyses. By including every subject who completed at least one assessment, we are not only more likely to conserve power, but also less likely to produce biased effect estimates. In mixed effects analyses, the slope of the outcome will be modeled as the key

dependent variable predicted by randomization group. We will conduct the analysis with and without conditioning on relevant baseline covariates. The results of these longitudinal analyses can be easily converted to a cross-sectional group effect at each assessment time point to describe the magnitude and significance of group differences. Of particular interest is the group difference at end of treatment (6-month assessment). The mixed effects analyses will be repeated using a model where the baseline scores on each outcome are treated as a baseline covariate to control for (instead of as a part of) the repeated measures. This model can be useful if there is a considerable heterogeneity between before and after treatment processes. We will also analyze the data using conventional ANCOVA treating the end point neurocognitive composite as the dependent variable and controlling for the baseline neurocognitive composite. Further analyses will be conducted using the same analysis models but with transformed data (e.g., log transformation) to check the sensitivity of the results to deviation from outcome normality. Statistical significance of all main effects and interaction terms as well as cross-sectional group differences will be determined using a one-tailed Type 1 error rate of α =.05. The same analysis strategy will be employed for secondary efficacy outcomes and a false discovery rate correction will be implemented to control inflation of Type 1 error.

If the exploratory biosample objectives are pursued, we will explore whether baseline peripheral blood levels of PTEN-associated pathway molecules (PI3K/AKT, mTOR, MAPK protein levels) change with treatment and if changes in peripheral pathway molecules correlate with clinical improvement. To determine whether PTEN-associated pathway molecules change with treatment, we will use a similar mixed effect (growth curve) modeling approach to that described above for Secondary Objective with screening, 3-month, and 6-month pathway measurements as outcome measures. The Time by Randomization Group interaction will test whether the everolimus treatment group shows improvement/normalization of PTEN-pathway molecule levels relative to placebo. This component will be dependent on securing additional funds.

In analyzing the resting state EEG and AEP data we will focus on the following:

- 1. Baseline EEG gamma power
- 2. AEP N1 habituation
- 3. AEP variability (phase-locking factor, also called intertrial phase coherence)

EEG and AEP analysis will occur via the Boston EEG Automated Processing Pipeline (BEAPP), created at Boston Children's Hospital by [name] MD. BEAPP is MATLAB-based software designed to facilitate batch processing of EEG files for artifact removal and signal processing in an automated manner. Users have the option to alter multiple settings, to customize processing to their needs. The pipeline is freely available and covered under a General Public License, which allows other groups to replicate or alter analyses for their own data if they wish.

To prepare EEG and AEP data for analysis, the pipeline imports EEG from various acquisition formats and electrode layouts into a standardized format. Data will first be processed via PREP, which removes 60 Hz line noise, identifies and interpolates bad channels, and references to average. Data will then be high pass filtered at 1 Hz, and will undergo artifact removal via MARA, an automated independent component-based supervised machine learning algorithm that handles artifacts including ocular artifact, muscle artifact, and loose electrodes.

For analysis of resting EEG data, segments of high-amplitude artifact (>150 uV) will be removed, and the remaining data will be segmented into 2-second epochs. Data will undergo a Laplacian transform, as this has been shown to reduce sensitivity of the EEG signal to contamination by myogenic activity, which is otherwise particularly prominent in the gamma band. Spectral analysis will be performed on each epoch with multitaper methods using 3 tapers, in order to determine the average power spectrum across all epochs. This will allow for determination of power in the gamma frequency band, particularly the 62-90Hz range.

For analysis of AEP data, data will be epoched into 2000 ms trials (-500 to 1500 ms), and baseline corrected using the 500 ms period prior to the first auditory stimulus in each trial. Any trial with amplitude exceeding 150 uV will be removed. N1 will be defined as the most negative-going waveform deflection between 50 and 150ms post-stimulus, over the central region. (If N1 cannot be adequately identified in this population using these criteria, independent components analysis will be used to identify the N1 component instead). Habituation of the N1 amplitude will be quantified as percent change from the first to second auditory click in each trial. Intertrial phase coherence (ITPC) will be calculated using the function *newtimef*, and reported as the maximum absolute value ITPC in the 50-150ms timeframe, in the alpha frequency band (8-12Hz).

Two approaches will be used to explore whether changes in PTEN-pathway molecules are correlated with changes in clinical improvement. First, we will use the mixed effects modeling framework to examine the correlation between the longitudinal changes in the neurocognitive composite score and changes in PTEN-associated pathway molecules. In this framework, the relationship between slopes representing individual clinical changes and individual PTEN-pathway molecule changes are estimated. We will also examine whether this correlation differs by treatment group. Second, we will estimate a structural model with cross-lagged relationships estimated between screening/3-month PTEN-pathway levels and 3-month/6-month efficacy measurements. Rather than evaluating the relationship between changes over time, the cross-lagged structural model examines whether pathway molecule levels at earlier time points predict efficacy measurements at later time points. Each of these methods will use all available data following the intent-to-treat principle. As a result, they are less likely to produced biased estimates than a bivariate correlation approach using changes from baseline because the latter method can only be computed for individuals with complete data.

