2.1 Primary objective

To evaluate the safety of everolimus compared with placebo in patients with PTEN mutations focusing on NCI CTCAE Grade 3 and 4 adverse events, serious adverse events, and Grade 3 and 4 laboratory toxicities. The primary endpoint will be study drop-out rate due to side effects, comparing everolimus vs. placebo. Based on the published literature and our experience in prior TSC trials we hypothesize that the drop-out rate due to side effects in those receiving everolimus will be similar to those in the placebo group with minimal effect size (< 10% difference). We will also determine the frequency of adverse events by type and severity. We predict that the rate of adverse events will be no more than 10% higher in the everolimus group compared to placebo, but overall severity will be minimal.

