4.3 Blinded Treatment Phase

All baseline procedures and evaluations should be completed within 6 weeks of the screening visit. If a patient's safety lab results are out of range, and the investigator has reason to believe there were situational factors affecting the values, the screening labs may be repeated. The safety evaluations may be completed at a lab that is geographically close to the participant and either provide the results of that analysis directly to the study team, or a sign a release so the study team can obtain the results from the lab. If a patient's baseline visit is more than 6 weeks after the screening visit the participant must have the safety labs re-drawn and processed, have the physical and neurological exam re-done, and the study team will confirm that there are no changes in the medical history or changes to the patient's current medications. If the screening safety evaluation and/or lab results are out-of-range, the participant will not be eligible to participate in the study. Patients who meet the study eligibility criteria following screening will be randomized to receive everolimus or placebo. The randomization ratio is 1:1, with one patient being randomly assigned to everolimus for every one patient randomly assigned to placebo. Treatment assignment via the RDCRN Members' Website should occur prior to the Baseline visit to allow adequate time for pharmacy preparation. Patients must start treatment within 7 days of the baseline visit, given that the participant still meets all inclusionary criteria and has not developed any exclusionary criteria. The medication should be taken at the same each day with a light, low-fat breakfast (i.e. 8:00 am with light breakfast).

The duration of blinded phase this study is 6 months. Patients will have their first daily dose of everolimus or placebo within 7 days of Visit 2 (baseline) and will continue on treatment for 6 months unless an intolerable toxicity occurs, withdrawal of consent, or investigator decision to discontinue the patient from study treatment.

Starting dose and adjustments are defined in Section. 6.2.

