7.5 Randomization Procedure

Subjects will be randomized 1:1 to everolimus or placebo after meeting all eligibility criteria. A designated member of the research team will communicate to the participant that randomization has occurred and sufficient study drug will be dispensed to cover the interval until the next study visit. This is a double-blind study. The study design allows patient unblinding during the double-blind phase only in very precise circumstances (section 7.6.1).

Randomization data are to be kept strictly confidential until the time of unblinding at discontinuation or at the time of final analysis. These data will not be accessible to anyone involved in the conduct of the study with the exception of the unblinded physicians, the Medical Monitor, the Data Safety and Monitoring Committee (DSMC), and the Data Management Coordinating Center (DMCC). The DSMC will review safety data as outlined in section 15. The identity of treatment arms will be concealed by the use of study drugs (everolimus and matching placebo) that are identical in packaging, labeling, schedule of administration and in appearance.

Prior to Baseline (Visit 2), the investigator or his/her designee will log onto the data system to verify that the patient fulfills all eligibility criteria and randomize the patient to a treatment arm. The system will assign a randomization arm, as described in the 7904 Manual of Procedures. The pharmacy will be responsible for dispensing the active drug or placebo based on the procedures outlined in the 7904 Pharmacy Manual of Procedures. The randomization will be stratified by age. Age will be stratified by two levels. Level 1 will be participants aged 5-21 years old, and level 2 will be 22-45 year olds. Permuted block sizes of two and four will be used. At the conclusion of the 6-month double-blind phase, the blind will be broken immediately. Individuals on the active drug will exit the study, and those who were on placebo will be invited to join the open label phase.

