17.1 Power Estimation

This is the first study to evaluate the efficacy of everolimus in patients with a PTEN mutation and ASD/DD. As such, analyses will be predominantly descriptive with the intent of generating plausible hypotheses to be tested in a Phase III confirmatory trial. The planned recruitment sample size of 40 was based on three considerations: 1) the expected recruitment potential of the three sites, 2) a desire to ensure sensitivity to any enrichment in side effects or problems with tolerability in everolimus treated patients, and 3) the need for adequate statistical power in examining primary and secondary efficacy outcomes. Assuming an overall dropout rate of approximately 10%, 44 patients will need to be enrolled to get 40 patients with complete trial data. However, following intent to treat procedures, all patients who are randomized, dosed, and for whom baseline data is collected will be included in statistical analyses. Statistical power considerations for each aim/hypothesis are described below. Except for safety analyses, where only everolimus-treated patients would be expected to show enrichment of dropout or side effects, statistical power estimates are based on one-tailed significance tests with Type 1 error rate of α =.05.

Primary Objective- Safety. The planned sample size of 40 is underpowered to detect small differences in dropout rates or side effects between everolimus versus placebo-treated groups. Statistical power will only be adequate if at least a 35% difference in the proportion of dropout/side effects is observed (1- β ≥.81), assuming a one-tailed Type 1 error rate of α =.05. This is equivalent to 1/20 patients experiencing an adverse event/side effect in the placebo arm and 8/20 in the treated arm. Similarly, statistical power of survival analyses will only be fair (1- β ≥.57) if a hazard ratio of 7.5 is observed, equivalent to a 5% dropout rate in the placebo group versus a 30% dropout rate in the everolimus group. However, because the goal is to maintain sensitivity to any potential enrichment in dropout or side effects, any indicator showing a difference of 10% or greater will be considered a meaningful difference and will be reported.

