Secondary Objective – Efficacy. For power estimation purposes, the variability in PTEN patients treated with an mTOR inhibitor is expected to be similar to the untreated sample. Preliminary data indicates that the measures which comprise the dominant portion of the neurocognitive composite index (processing speed working memory, and fine motor) are highly sensitive to the brain dysfunction seen in PTEN patients with ASD. The effect sizes are approximately 1 SD or larger. In a comparison between mTOR treated vs. untreated PTEN patients, an effect size of at least 0.65 SD would be of interest and represent clinically- meaningful improvement. For example, an effect size of at least 0.65 SD on cognitive measures would translate to a 10-point standard score improvement in the everolimus-treated group relative to placebo. An improvement of 10 or more points is outside the standard error of measurement for most cognitive measures and is typically considered a reliable change when disordered populations are re-tested.

A sample size of 40 (20 per arm) patients will permit detection of endpoint (6-month follow-up) differences of at least 0.80 SD at the 5% significance level (one-sided alpha = 0.05) with 80% power (1- β). Statistical power will be weaker (1- β =.65) if smaller cross-sectional differences are observed (0.65 SD). However, statistical power is very strong, even for smaller differences (Cohen's d≥.50 equivalent to ≥.50 SD difference) when the full repeated measures nature of the design is considered – baseline, 3-month follow-up, 6-month follow-up. Assuming even modest correlations between repeated measurements of outcome variables (r≥.30), power to detect clinically meaningful differences of .50 SD is very good (1- β =.83; one-sided α =.05). If the primary outcome measure (neurocognitive composite) meets nominal statistical significance in the expected direction (one-tailed p<.05) or a secondary outcome measure meets a more stringent false discovery rate-corrected

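### Pre-specifying Boschloo's exact test for the drop-out and side-effect comparisons would be a cheap gain in sensitivity over the unspecified chi-square-or-Fisher rule

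*Combined protocol and SAP*

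**What the plan says.** Section 2.1 defines the endpoint: "The primary endpoint will be study drop-out rate due to side effects, comparing everolimus vs. placebo". For objective 1, section 17 gives the test: "We will use chi-square statistics (or Fisher's exact test depending on cell counts) to compare dropout and rates of specific side effects". It sets the level: "Statistical significance will be determined using a one-tailed test Type 1 error rate of α=.05". No cell-count threshold is stated for moving from one test to the other. Section 17 also declines a false discovery rate correction for these comparisons, on the ground that sensitivity to any excess of side effects should be as high as possible.

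Section 17.1 works with 20 per arm ("A sample size of 40 (20 per arm) patients") and gives the expected drop-out: "Assuming an overall dropout rate of approximately 10%, 44 patients will need to be enrolled to get 40 patients with complete trial data". It says that the sample is too small to detect small safety differences. It puts power at .81 or more only for a 35-point difference, illustrated by 1/20 on placebo against 8/20 on everolimus. It adds that any indicator differing by 10% or more will be treated as meaningful and reported.

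**The concern.** The primary endpoint will produce few events. Fisher's test conditions on the total number of events, so with few events it has only a handful of attainable p-values and its true error falls far below the nominal .05. That sits badly with the plan's wish for sensitivity, because part of the allowed error goes unused.

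The unwritten switch matters too. At 4 v 0 with 20 per arm, the uncorrected chi-square gives a one-sided p of .018 and Fisher gives .053. The significance statement for the primary endpoint could then depend on a rule that is not in the plan. What is at stake is how a modest excess of drop-outs on everolimus is labelled, and some power that can be recovered without extra patients.

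**Working it through.** **Inputs.** 20 per arm and about 10% overall drop-out (17.1); one-sided .05 (17); 1:1 allocation (4.3); permuted blocks of two and four within two age strata (7.5).

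**Formulas.** Let a and b be the events on everolimus and placebo.

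- Fisher, one-sided: p_F(a,b) = sum over k ≥ a of C(20,k)·C(20,a+b−k)/C(40,a+b).
- Boschloo: p_B(a,b) = maximum over a common rate π of P_π{p_F(A,B) ≤ p_F(a,b)}.
- Power: the sum, over all 21 × 21 tables with p ≤ .05, of Bin(a;20,p_E)·Bin(b;20,p_P).

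**Step 1: the plan's own figure.** At 40% v 5%, one-sided Fisher power is .808, which matches the stated .81. The one-sided uncorrected chi-square gives .897 and the pooled normal approximation .866. The plan's power statement is therefore consistent with Fisher.

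**Step 2: which test applies.** 10% of 40 is 4 drop-outs, an expected 2 per arm. That is below the customary threshold of 5 (an assumption, since the plan gives none). The 10% covers drop-out for any reason, so drop-outs due to side effects would number four or fewer.

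**Step 3: small tables at 20 per arm.** For 4 v 0, Fisher gives C(20,4)/C(40,4) = 4,845/91,390 = .0530. For 3 v 0 it gives 1,140/9,880 = .115.

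| Everolimus v placebo | Fisher p | Boschloo p |
|---|---|---|
| 3 v 0 | .115 | .077 |
| 4 v 0 | .053 | .030 |
| 5 v 0 | .024 | .011 |
| 5 v 1 | .091 | .052 |
| 6 v 1 | .046 | .023 |
| 7 v 2 | .064 | .040 |

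**Step 4: true error at nominal .05, 20 per arm.**

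| Common rate | Fisher | Boschloo |
|---|---|---|
| 5% | .001 | .006 |
| 10% | .008 | .020 |
| 20% | .023 | .037 |
| Maximum over all rates | .027 | .043 |

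The uncorrected chi-square reaches .054, so it does not hold the level. Boschloo rejects all 119 tables that Fisher rejects and 11 more.

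**Step 5: power, 20 per arm.**

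| Everolimus v placebo | Fisher | Boschloo |
|---|---|---|
| 10% v 5% | .020 | .052 |
| 15% v 5% | .088 | .156 |
| 20% v 5% | .21 | .30 |
| 30% v 5% | .54 | .63 |
| 40% v 5% | .81 | .86 |

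**Step 6: other arm sizes.** For 4 v 0, Fisher gives .042 with 19 everolimus and 21 placebo (3,876/91,390), and .065 with 21 and 19. Boschloo gives .022 and .043. With 22 per arm (44 enrolled), Fisher gives .054 and Boschloo .029, with maximum true error .025 and .049.

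**The case against.** The strongest reply is that nothing is broken. Fisher's test is valid and standard for sparse tables. The plan calls itself exploratory and mainly descriptive, and admits low power for safety. It adds Kaplan-Meier, Cox and logistic analyses of drop-out, and ties no decision to this p-value. All of that stands and sets the weight of the point.

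A reader might infer that the trial would be blind to four drop-outs on everolimus and none on placebo. The documents do not support that, for three reasons. First, 4/20 v 0/20 is a 20-point difference, which 17.1 would report under its 10% rule whatever the p-value. Second, four is the expected number of drop-outs for any reason. For drop-out due to side effects the plan predicts arms less than 10 points apart, which is fewer than two patients in 20. Third, Fisher's failure at 4 v 0 is not a fixed property of the design: it holds at 20:20, but with 19 everolimus and 21 placebo Fisher rejects. Nor do the documents say that Fisher will be used; that is inferred from the low counts and the match in power.

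The gain is also limited where events are fewest. Among tables with six or fewer events at 20 per arm, only 4 v 0 changes from non-significant to significant. Boschloo is not the only candidate either. Barnard's test with pooled Z gives .043 at 3 v 0 and has the same maximum error of .043, although its power at 40% v 5% is slightly lower (.856 v .863). Boschloo's advantage is that by construction it cannot lose a Fisher rejection. Whichever test is chosen must be fixed in advance.

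**Conclusion.** The point holds as a low-cost improvement to a valid analysis. At 20 per arm, Boschloo adds about 5 to 9 percentage points of power for true differences of 15 to 35 points, and it moves 4 v 0 from .053 to .030. It also removes a choice of test that depends on the data and has no stated rule.

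The price is a higher true false-positive rate: the maximum goes from .027 to .043, still below .05. The two tests share the nominal ceiling, not the actual error rate. 3 v 0 (.077) and 5 v 1 (.052) remain non-significant, and power for differences of 10 points or less stays very low under either test.

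The conclusion assumes that Fisher would be the test used and that the arms are close to 20 each.

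**What to change.** In section 17, objective 1, replace the chi-square-or-Fisher choice with a one-sided Boschloo unconditional exact test at .05, for drop-out and for each specific side effect, whatever the cell counts. In 17.1, restate the power for 5% v 40% as .86. Keep the rule that differences of 10% or more are reported regardless of significance.

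The cost is one sentence and one figure. The test is available in standard software, and nothing changes in the sample size, the conduct of the trial or patient management. The amended text should say that the true error rate is higher than with Fisher, though under the same ceiling.
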